4.4.2.1 Phase 1b: Dose-escalation

Patients will receive alvocidib administered in sequence after fixed doses of either DEC or AZA using a standard 3+3 design according to the dose cohorts in *Table 5* and *Table 6*.

Table 5: Proposed Dose Escalation Schema (DEC + Alvocidib)

Dose Level ^a	Days 1-5, Decitabine	Day 8, Alvocidib ^b	
	1-hr IV infusion	30-min bolus	4-hr IV infusion
1	20 mg/m ²	20 mg/m ²	20 mg/m ²
2	20 mg/m ²	30 mg/m ²	30 mg/m ²
3	20 mg/m ²	30 mg/m ²	45 mg/m ²
4	20 mg/m ²	30 mg/m ²	60 mg/m ²

a It is possible for additional and/or intermediate dose levels to be added during the course of the study.

b Alvocidib to be administered first as a 30-minute (\pm 10 minutes) IV bolus followed up to 30 minutes later by a 4-hour (\pm 15 minutes) IVI.

Two separate cohorts of patients (minimum of 6 patients; 3 per cohort) will receive AZA followed by alvocidib administered as a **30- to 60-minute** IVI according to the dose cohorts in **Table 6**.

Table 6: Proposed Dose Schema (AZA + Alvocidib)

Dose Level ^a	Azacitidine ^b	Day 10, Alvocidib
	IVI or SC injection ^c	30- to 60-min IVI
1A	75 mg/m ²	75 mg/m ²
1B	75 mg/m ²	90 mg/m ²

a It is possible for additional and/or intermediate dose levels to be added during the course of the study.

b AZA can be administered on either a 7-day or 5-2-2 schedule.

c AZA may be given as an IVI over 10 to 40 minutes or an SC injection.

The first 2 patients at a dose level may be treated simultaneously and the third patient will be treated after 14 days so long as the initial 2 patients have not experienced any unacceptable drug-related toxicity. Once the last patient enrolled has completed Day 28 without observation of a DLT and the next higher alvocidib dose level has not yet been studied, the alvocidib dose will be increased in a new 3-patient cohort.

If 1 of 3 patients in a cohort experiences a DLT, up to 3 additional patients will be treated at that dose level. If no additional DLTs are observed in the expanded 3- to 6 patient cohort within 28 days after the last patient was first dosed, the dose will be escalated in a new cohort of 3 patients. If 2 or more of 3-6 patients at a given dose level experience a DLT during the first cycle, then the MTD will have been exceeded and up to a total of 6 patients will be treated at the previous lower dose level. If 0 or 1 of 6 patients experiences a DLT at this previous lower dose level, this dose will be declared the MTD.

The MTD is defined as the dose at which \leq 1 of 6 patients experience a DLT during Cycle 1 with the next higher dose having at least 2 of 3 to 6 patients experiencing a DLT during Cycle 1. Adverse events meeting the definition of DLT during Cycles 2+ will be taken into consideration when evaluating dose escalation.

4.4.2.2 Expansion at MTD/RP2D

Once the MTD or preliminary RP2D of alvocidib administered as a **30- to 60-minute** IVI is identified, up to 25 patients will be enrolled in an Expansion cohort to receive alvocidib following AZA to confirm safety, explore potential biomarkers, and evaluate potential signals of alvocidib activity.

Once this Expansion cohort is completed, the study will progress to Phase 2.

4.4.2.3 Phase 2

The Phase 2 study will then commence in a Simon 2-stage minimax design [27] using the RP2D of alvocidib administered as a **30- to 60-minute** IVI determined from the Phase 1b study to explore the efficacy of alvocidib when administered in sequence after AZA.

- Stage 1: Up to 15 evaluable patients will be enrolled and treated at the RP2D identified in the Phase 1b study. Stage 2 may be initiated at any point after confirming a response (CR/CRi/CRmarrow/PR/HI) in two Stage 1 patients. If there is ≤ 1 responder among 15 evaluable Stage-1 patients, the study will be stopped after Stage 1.
- Stage 2: Ten patients will be enrolled to bring the total enrollment in Phase 2 (including Stage-1 patients) to 25 evaluable patients. Stage-2 patients will also receive the RP2D dose of alvocidib administered as a **30- to 60-minute** IVI identified in the Phase 1b study.

Enrollment into Phase 2 may be stopped at any point once ≥ 6 patients have had a response to treatment, but the maximum enrollment in Phase 2 will be 25 evaluable patients.

The study may be stopped early during Phase 2 in the event of unacceptable toxicities. Early stopping rules for safety are based on a Sequential Probability Ratio Test (SPRT) with a baseline toxicity rate of 5%; an upper ceiling of unacceptable toxicity of 20% (ie, toxicities meeting one or more DLT criteria as stated in [Section 4.5.3](#)); and alpha=0.05 with power=80%.

The study will be stopped if unacceptable toxicities are observed in:

- 2 of the first 2 patients
- 3 of the first 11 patients
- 4 of the first 20 patients
- 5 of the first 29 patients (Ph 2 study to enroll maximum of 25 patients, but considering possible replacement patients)

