4. INVESTIGATIONAL PLAN

4.1 OVERALL STUDY DESIGN

This is a Phase 1b/2, open-label, safety, efficacy, PK, and pharmacodynamic (PD) study.

Phase 1b

Patients will be enrolled in cohorts of 3-6 patients. Escalation of the alvocidib dose will follow a standard 3+3 design with sequential cohorts of 3 patients treated with incrementally higher doses of alvocidib administered in sequence after DEC (**during dose escalation**) or AZA until a DLT is observed and the MTD is established ([Section 4.5.3](#)). The first 2 patients at a dose level may be enrolled simultaneously and the third patient will be enrolled after 14 days so long as the 2 initial patients have not experienced any unacceptable toxicity.

If 1 of 3 patients in a cohort experiences a DLT, up to 3 additional patients will be treated at that dose level. If no additional DLTs are observed in the expanded 3- to 6-patient cohort within 28 days after the last patient was first dosed, the dose will be escalated in a new cohort of 3 patients. If 2 or more of 3-6 patients at a given dose level experience a DLT during the first cycle, then the MTD will have been exceeded and up to a total of 6 patients will be treated at the previous lower dose level. If 0 or 1 of 6 patients experiences a DLT at this previous lower dose level, this dose will be declared the MTD.

The MTD is defined as the dose at which ≤ 1 of 6 patients experience a DLT during Cycle 1 with the next higher dose having at least 2 of 3 to 6 patients experiencing a DLT during Cycle 1. Adverse events meeting the definition of DLT during Cycles 2+ will be taken into consideration when evaluating dose escalation.

Once the MTD or preliminary RP2D of alvocidib administered via hybrid dosing (ie, IV bolus followed by IVI) is identified, 2 cohorts of at least 3 patients each will receive AZA followed by alvocidib administered as a **30- to 60-minute** IVI.

Expansion at MTD

Once the MTD or preliminary RP2D of alvocidib administered as a **30- to 60-minute** IVI is determined, up to 25 patients will be enrolled in an Expansion cohort to receive alvocidib following AZA to confirm safety, explore potential biomarkers, and evaluate potential signals of alvocidib activity. Once this Expansion cohort is completed, the study will progress to Phase 2.

Phase 2

The Phase 2 design is based on the Simon 2-stage minimax design [27].

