11.11 INTERIM ANALYSIS

For Phase 1b, safety data will be monitored continuously per standard Phase 1 oncology study practices.

For Phase 2, because the Simon 2-stage minimax design will be employed, response rate data will be assessed after Stage 1 and Stage 2.

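### The Expansion cohort has no prespecified numerical toxicity trigger and no stated condition for moving to Phase 2; the only numerical safety boundary starts in Phase 2 and does not count Expansion DLTs

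*Protocol*

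**What the plan says.** Protocol 4.4.2.2 opens Expansion once the MTD or a preliminary RP2D of the short infusion is known: "up to 25 patients will be enrolled in an Expansion cohort to receive alvocidib following AZA to confirm safety", among other aims. The next step is "Once this Expansion cohort is completed, the study will progress to Phase 2". Protocol 4.1, 4.3.1 and 11.2 and SAP sections 2 and 4 carry the same progression statement. None of them adds a DLT count, a rate or a go/no-go criterion.

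The numerical safety rule is introduced in protocol 4.4.2.3 with "The study may be stopped early during Phase 2 in the event of unacceptable toxicities". It is a sequential probability ratio test (SPRT) of 5% against 20%, with alpha 0.05 and power 80%, and it stops at 2 of 2, 3 of 11, 4 of 20 or 5 of 29 patients. The event is a toxicity meeting the DLT criteria of 4.5.3. The last step is explained by Phase 2 enrolment plus replacements, so Expansion patients are not in the count.

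For the earlier part, protocol 11.11 says "For Phase 1b, safety data will be monitored continuously per standard Phase 1 oncology study practices". SAP 7.1 extends this to dose expansion.

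**The concern.** Expansion and Phase 2 are alike in population (untreated de novo or secondary MDS, protocol 4.3.2), in size (up to 25 each) and, as 4.4.2.2 describes it, in drug sequence and infusion. Only the later part has a numerical limit.

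The 3+3 rule does not fill the gap. It governs cohorts of 3 to 6, and protocol 4.1 plans the azacitidine cohorts as "2 cohorts of at least 3 patients each will receive AZA followed by alvocidib administered as a" a short infusion. Expansion may also open on a preliminary RP2D, for which no minimum number of patients is stated.

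Two things are at stake. The larger group treated at the selected dose has no agreed count at which someone must stop and look. And an aim of confirming safety has no written result that would lead anywhere other than Phase 2.

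**Working it through.** **Inputs.** p0 = 0.05, p1 = 0.20, alpha = 0.05, beta = 0.20 and the four boundary points (protocol 4.4.2.3); 25 Expansion patients over 6 to 8 months (synopsis); DLTs judged in Cycle 1 (4.5.3), with a 28-day wait in escalation (4.4.2.1). The true rates of 1/6 and 1/3 are assumptions; the documents give only 5% and 20%.

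**1. Reproduce the plan's boundary.** A Wald SPRT stops when DLTs ≥ h + s·n.
- ln odds ratio = ln[(0.20×0.95)/(0.05×0.80)] = ln 4.75 = 1.558
- h = ln(0.80/0.05)/1.558 = 2.773/1.558 = 1.779
- s = ln(0.95/0.80)/1.558 = 0.1719/1.558 = 0.1103
- Largest n for k events = (k − h)/s: 2.0, 11.07, 20.13 and 29.20 for k = 2, 3, 4 and 5

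Rounded down, these are 2, 11, 20 and 29, an exact match. At n = 25 the limit is 1.779 + 0.1103×25 = 4.54, so 5 DLTs.

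**2. Expansion as written.** Expected DLTs = 25p: 1.25 at 5%, 5.0 at 20%, 8.3 at 1/3. At 20%, the exact binomial P(5 or more of 25) is 57.9%. That count meets the Phase 2 limit at n = 25, yet Phase 2 would start counting from zero.

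**3. The same boundary applied to 25 Expansion patients.** Exact patient-by-patient recursion, independent DLTs, crossing at 2 DLTs by n = 2, 3 by n = 11, 4 by n = 20, or 5 by n = 25. Mean DLTs = p × mean patients. Means include cohorts that never cross.

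| True DLT rate | P(trigger) | Mean patients, no lag | Mean DLTs, no lag | Expected DLTs as written |
|---|---|---|---|---|
| 5% | 2.7% | 24.6 | 1.2 | 1.25 |
| 1/6 (assumed) | 51.8% | 18.7 | 3.1 | 4.2 |
| 20% | 67.5% | 16.4 | 3.3 | 5.0 |
| 1/3 (assumed) | 96.9% | 9.4 | 3.1 | 8.3 |

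**4. Allow for reporting lag.** Enrolling 25 patients in 6 to 8 months, at 30.4375 days a month, gives 25/6.52 = 3.8 down to 25/8.70 = 2.9 per 28 days. So about 3 to 4 more patients enter before a DLT status is settled. Adding 3 to 4 patients after each crossing, capped at 25:
- at 20%: 3.7 to 3.8 mean DLTs
- at 1/3: 12.2 to 13.2 mean patients and 4.1 to 4.4 mean DLTs

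P(trigger) is unchanged.

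**5. Prior protection from 3+3.** P(at most 1 DLT in 6) at a 20% rate = 0.80^6 + 6×0.20×0.80^5 = 0.262 + 0.393 = 65.5%. A dose at the ceiling usually passes.

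**The case against.** The strongest reply is that Expansion is not unsupervised and its toxicity is not discarded.
- Protocol 4.3.2 and 4.4.2 place Expansion inside Phase 1b, and Phase 2 uses the RP2D from Phase 1b. A preliminary RP2D can therefore be changed, and 4.2 says later-cycle toxicity is weighed in setting it.
- The Medical Monitor authorizes each enrolment (4.2), the dose escalation committee sees full safety profiles and can act (11.10), monitoring is continuous (11.11, SAP 7.1), and 6.4 gives general grounds for termination.

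All of this stands. A reader might infer from the progression sentence that Phase 2 must open whatever Expansion shows, that its DLTs are ignored, or that nobody could stop the cohort. The documents do not support those readings. What is missing is narrower: none of these provisions states a threshold, and none says how Expansion DLTs would change the RP2D or hold back Phase 2.

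Two further objections also stand in part. The no-lag exposure figures flatter the boundary, so the lagged ones are the fairer guide. And a boundary built on a 5% baseline fits awkwardly with a 3+3 rule that can accept 1 DLT in 6; at that true rate it would pause about half of cohorts. That argues for pause and review rather than automatic stopping. It does not argue for having no number, since the same oversight provisions did not keep the sponsor from setting one for Phase 2.

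**Conclusion.** The point holds as a gap in prespecification: no numerical trigger, no condition on progression, and no statement on carrying DLTs forward.

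At the protocol's own 20% ceiling, a full Expansion cohort would reach a Phase 2 stopping count 58% of the time without any written consequence. The existing boundary would have flagged 67.5% of such cohorts, with mean DLTs falling from 5.0 to about 3.7 to 3.8 after lag. At an assumed rate of 1/3 it would flag 97%, with 12 to 13 patients treated on average instead of 25.

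These figures assume independent DLTs, a constant true rate and no resumption after a pause; if review lets enrolment resume, the reduction in exposure is smaller. The comparison with Phase 2 also assumes the same dose in both parts and an azacitidine-only Expansion, on which the documents disagree (see the fix).

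The SAP records that the study closed on November 17, 2020 with no patients in Expansion or Phase 2. No collected data and no planned table are affected, so this is a design lesson and not a threat to the reported results.

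**What to change.** In protocol 4.1, 4.4.2.2 and 11.2, with the synopsis and 4.3.1 aligned:
1. Apply the boundary already in the protocol to Expansion patients at the same dose, as a trigger to pause enrolment for a documented dose escalation committee review.
2. Make progression to Phase 2 conditional on no crossing, or on that review supporting it.
3. State whether Expansion DLTs at the RP2D count toward the Phase 2 boundary.
4. Reconcile the descriptions of the Expansion backbone. Protocol 4.1 and 4.4.2.2 and SAP section 2 name azacitidine only; protocol 2.6 and 11.2 and SAP section 4 allow either hypomethylating agent.

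The cost is wording, with no new data or patients. The downside is pauses that prove unnecessary: 2.7% of cohorts at a true rate of 5%, and 52% at 1/6. With the study closed, matching edits to SAP sections 2 and 4 would only keep the documents consistent.

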4.5 MANAGEMENT OF TOXICITIES AND DOSE MODIFICATIONS

Suggested doses of supportive care therapies are provided; however, adjustment of the dosages based on the patient's clinical condition or each institution's standard of care is permitted.

Adverse events may be treated with concomitant medications, as deemed clinically indicated by the Principal Investigator (PI). All concomitant medications must be recorded in the source and on the appropriate case report form (CRF).

Adverse events that are moderate to severe in intensity (see **Section 8.1 for intensity assessment when NCI CTCAE grade [Appendix D] is not available**) and considered possibly or probably related to study drug treatments may result in the delay or termination of study treatment in affected patients. Such termination should be reviewed with the Sponsor's Medical Monitor at the earliest possible time (see **Section 8.5**). Following review with the Sponsor's Medical Monitor, the study patient may be permanently withdrawn from the study depending upon the nature and severity of the event.

4.5.1 Management of Nonhematologic Toxicities

4.5.1.1 Hyperkalemia and Tumor Lysis Syndrome

Tumor lysis may occur as part of initial cytoreductive therapy. The most extreme form, known as Tumor Lysis Syndrome (TLS), is characterized by hyperkalemia, hyperuricemia, hyperphosphatemia, increased lactate dehydrogenase (LDH), coagulopathy, and a potential cytokine release syndrome. Preventative measures to reduce the likelihood of developing TLS include ensuring adequate hydration of patients prior to administration of alvocidib as well as careful monitoring of laboratory parameters before and after infusion. Investigators should follow their own institutional protocols in determining the best treatment for patients with symptoms of TLS.

4.5.1.1.1 TLS Prophylaxis for DEC + Alvocidib

Tumor lysis syndrome prophylaxis for patients receiving alvocidib in sequence following DEC should follow each institution's standard of care.

4.5.1.1.2 TLS Prophylaxis for AZA + Alvocidib

All patients receiving alvocidib in sequence following AZA will receive TLS prophylaxis as detailed below:

- IV Hydration
 - Prior to AZA
 - IV hydration according to each institution's standard of care

- Prior to Alvocidib
 - Mandatory IV hydration with 0.45% NaCl (or similar hydration fluid per institutional standard) sterile solution at 500 cc for 1-2 hours prior to alvocidib, then an additional 500 cc for 1-2 hours after alvocidib during Cycle 1 (volume may be reduced to between 250 cc-500 cc, if clinically indicated). Hydration is optional for subsequent cycles.
- Diarrhea Prophylaxis
 - During AZA and Alvocidib Dosing
 - Replace excessive fluid losses, including from diarrhea, unless otherwise clinically indicated.
 - Alvocidib-specific Measures
 - Alvocidib can induce diarrhea when given over a short period of time. Over-the-counter measures are typically effective in this setting if initiated early (see [Section 4.5.1.2](#)).
 - Persistent diarrhea despite optimal outpatient management would trigger medical consultation. Early consideration should be given for possible *Clostridioides difficile* (*C. difficile*) infection in this patient population and identifying/treating as expeditiously as possible is imperative (see [Section 4.5.1.2](#)).
- Oral Allopurinol
 - Mandatory oral allopurinol to be started on Day 1 of Cycle 1 and continued daily for first 2 weeks (ie, 14 days). This may be discontinued for subsequent treatment cycles if uric acid levels are within normal limits and there is no evidence of TLS.
- Oral Phosphate Binder
 - Mandatory oral phosphate binder to be started on Day 1 of Cycle 1 and continued daily for the first 2 weeks (ie, 14 days).
 - If serum phosphorus levels are <3 after the first treatment with alvocidib and there is no evidence of TLS, phosphate binders may be discontinued. Patients should continue to be monitored for TLS as outlined for subsequent treatment cycles. Caution is warranted for patients who still have a high blast count as they remain at risk for TLS with subsequent treatments.

- Laboratory Evaluations for Tumor Lysis Syndrome ('tumor lysis labs')
 - Tumor lysis labs include electrolytes (sodium, potassium, chloride, and carbon dioxide) as well as creatinine, calcium, lactate dehydrogenase (LDH), uric acid, and phosphorus levels
 - During Cycle 1
 - Monitor tumor lysis labs prior to AZA and 2 hours (± 30 minutes) after completion of AZA dosing
 - Monitor tumor lysis labs prior to alvocidib IVI and 2 hours (± 30 minutes) after completion of IV hydration post alvocidib.
 - All tumor lysis labs should be drawn, however the potassium level obtained at 2 hours post dose (AZA) and 2 hours post hydration (alvocidib) should be reviewed immediately to determine if additional treatment is warranted.
 - Labs will also be drawn daily for the first 2 days following alvocidib (ie, Days 11-12) and at least weekly for the remainder of Cycle 1
 - During Cycle 2, tumor lysis labs will be assessed:
 - Prior to C2D1 first AZA dose and at 2 hours post C2D1 AZA dose
 - Prior to C2D10 alvocidib IVI and 2 hours (± 30 minutes) after completion of alvocidib IVI.
 - During Cycles 3+, tumor lysis labs will be checked at the discretion of the investigator in relation to patient blast counts

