	
Additional cycles may be considered following discussions between the investigators and the Medical Monitor.
 
Supportive care measures for all patients to include:
 
• Infection prevention (antibiotics, antifungals, antivirals) according to institutional standards• Routine growth factor support is not allowed. Growth factor support can be given at the discretion of the Investigator and with the Medical Monitor's approval in the presence of life threatening infection with ongoing neutropenia. 
TLS Prophylaxis (DEC + ALV)
 
• All patients receiving DEC (during dose escalation) will receive TLS prophylaxis as per each institution's standard of care 
TLS Prophylaxis (AZA + ALV)
 
All patients receiving alvocidib in sequence following AZA will receive TLS prophylaxis as detailed below:
 
• IV Hydration
○ Prior to AZA
▪ IV hydration according to each institution's standard of care○ Prior to Alvocidib
▪ Mandatory IV hydration with 0.45% NaCl (or similar hydration fluid per institutional standard) sterile solution at 500 cc for 1-2 hours prior to alvocidib, then an additional 500 cc for 1-2 hours after alvocidib during Cycle 1 (volume may be reduced to between 250 cc-500 cc, if clinically indicated). Hydration is optional for subsequent cycles.• Diarrhea Prophylaxis
○ During AZA and Alvocidib Dosing
▪ Replace excessive fluid losses, including from diarrhea, unless otherwise clinically indicated.○ Alvocidib-specific Measures
▪ Alvocidib can induce diarrhea when given over a short period of time. Over-the-counter measures are typically effective in this setting if initiated early.▪ It is strongly suggested that patients take 2 tablets of loperamide, 2 mg each (or equivalent), prior to the alvocidib IVI and then take 1 tablet (2 mg) for every loose stool up to a maximum of 8 tablets (16 mg) in a 24-hour period.▪ Persistent diarrhea despite optimal outpatient management would trigger medical consultation. Early consideration should be given for possible Clostridioides
--	---

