	
difficile (C. difficile) infection in this patient population and identifying/treating as expeditiously as possible should be top of mind.
 
• Oral Allopurinol
◦ Mandatory oral allopurinol to be started on Day 1 of Cycle 1 and continued daily for the first 2 weeks (ie, 14 days). This may be discontinued for subsequent treatment cycles if uric acid levels are within normal limits and there is no evidence of tumor lysis syndrome.• Oral Phosphate Binder
◦ Mandatory oral phosphate binder to be started on Day 1 of Cycle 1 and continued daily for the first 2 weeks (ie, 14 days).◦ If serum phosphorus levels are <3 after the first treatment with alvocidib and there is no evidence of TLS, phosphate binders may be discontinued. Patients should continue to be monitored for TLS as outlined for subsequent treatment cycles. Caution is warranted for patients who still have a high blast count as they remain at risk for TLS with subsequent treatments.• Laboratory Evaluations for Tumor Lysis Syndrome ('tumor lysis labs'):
◦ Tumor lysis labs include electrolytes (sodium, potassium, chloride, and carbon dioxide) as well as creatinine, calcium, lactate dehydrogenase (LDH), uric acid, and phosphorus levels◦ During Cycle 1
▪ Monitor tumor lysis labs prior to first AZA and 2 hours (\pm30 minutes) after completion of first AZA dose▪ Monitor tumor lysis labs prior to alvocidib IVI and 2 hours (\pm30 minutes) after completion of IV hydration post alvocidib.▪ All tumor lysis labs should be drawn; however, the potassium level obtained at 2 hours post first AZA dose and 2 hours post hydration following alvocidib IVI should be reviewed immediately to determine if additional treatment is warranted (see Section 4.5.1.2).▪ Labs will also be drawn daily for the first 2 days following first AZA dose (ie, Days 2-3) and alvocidib (ie, Days 11-12) and at least weekly for the remainder of Cycle 1.◦ During Cycle 2, tumor lysis labs will be assessed:
▪ Prior to C2D1 first AZA dose and at 2 hours post C2D1 AZA dose
--	--

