5.2.2 Cycles 2+

5.2.2.1 Cycles 2+: At Least 2 Hours Prior to First Dose of Alvocidib in Patients Receiving AZA + Alvocidib

During Cycles 2+, pretreatment IV hydration, oral allopurinol, and oral phosphate binder may be discontinued in patients receiving AZA and alvocidib if serum uric acid and phosphorus levels are within normal limits and there is no evidence of TLS.

Should TLS be suspected during subsequent cycles, perform the following procedures at least 2 hours prior to alvocidib dosing on Day 10 (unless otherwise stated):

- Initiate supportive care measures prior to first dose of alvocidib in patients receiving AZA + alvocidib to minimize the likelihood of TLS:
 - Administer pretreatment IV hydration and determine if oral allopurinol and oral phosphate binder are still clinically indicated (see [Section 4.5.1.1.2](#) and [Appendix A-3](#))
 - Assess patient for adequate hydration at all study visits and replace excessive fluid losses, including from diarrhea, unless otherwise clinically indicated ([Section 4.5.1.2](#) and [Section 4.5.1.3](#))

5.2.2.2 Cycles 2+ – Day 1

Perform the following activities and evaluations on Day 1 of Cycles 2+:

- Perform an abbreviated physical examination including weight (kg) and calculation of BSA
- Assess ECOG PS ([Appendix B](#))
- Record vital signs (temperature, heart rate, systolic and diastolic blood pressures) prior to first dose
- Collect blood for evaluation of laboratory parameters ([Appendix E](#)):
 - Hematology panel
 - Full serum chemistry panel
 - Tumor lysis labs required just prior to C2D1 AZA dose and 2 hours post C2D1 AZA dose ([Appendix A-3](#))

- Collect peripheral blood for PD analyses ([Section 7.4, Table 9 and Table 10](#))
- Collect urine or serum sample for β-hCG pregnancy test for females of child-bearing potential
- Administer prophylactic antibiotics, antivirals, antifungals, antiemetics, antidiarrheals according to standard practices at each investigational site
- Administer DEC on Days 1-5 (***during dose escalation***) or AZA on 7-day or 5-2-2 schedule according to [Section 4.4.2.1](#)
- Assess for AEs
- Record only those medications (prescription, nonprescription, nutritional supplements) administered in conjunction with an AE.

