- h If K+ levels are increasing to >4.0 mEq/L, patients should receive a 30 gm dose of sodium polystyrene sulfonate, unless there are other likely causes of hyperkalemia other than TLS or contraindication to its use. If potassium levels rise to >5.0 mEq/L, in addition to the 30 gm dose of sodium polystyrene sulfonate, patients should also receive 10 units of IV rapid-acting insulin and 25 gm (1 ampule) of IV dextrose 50%, unless there are other likely causes of hyperkalemia other than TLS or contraindication to its use. Investigators are strongly encouraged to consider patient hospitalization for inpatient monitoring and follow up. If potassium levels rise to >5.5 mEq/L, patients should be considered for emergent intermittent or continuous dialysis. Calcium supplementation should only be given for symptomatic hypocalcemia in this setting to avoid renal precipitation of calcium phosphate crystals. Patients who develop clinical evidence of cytokine release syndrome or who have hyperkalemia requiring dialysis will receive immediate steroid therapy with an equivalent of at least 20 mg of IV dexamethasone.
- i Tumor lysis labs to also be drawn on Days 2 and 3 prior to AZA doses during Cycle 1.

- j Mandatory IV hydration with 0.45% NaCl (or similar hydration fluid per institutional standard) sterile solution at 500 cc for 1-2 hrs prior to alvocidib, then an additional 500 cc for 1-2 hrs after alvocidib during Cycle 1 (volume may be reduced to between 250 cc – 500 cc, if clinically indicated). Hydration is optional for subsequent cycles.
- k Continue oral phosphate binder daily on Days 1-14 of Cycle 1.
- l Assess tumor lysis labs prior to alvocidib IVI and 2 hrs (\pm 30 mins) after completion of IV hydration post alvocidib.
- m Potassium levels obtained as part of the tumor lysis lab panel at 2 hrs after completion of IV hydration post alvocidib should be reviewed immediately for indications of tumor lysis syndrome as additional treatment may be warranted (footnote 'h').
- n Tumor lysis labs to be drawn daily for the first 2 days following alvocidib IVI (ie, Days 11-12) and at least weekly for the remainder of Cycle 1.
- o Oral allopurinol may be discontinued for subsequent treatment cycles if uric acid levels are within normal limits and there is no evidence of TLS.
- p Oral phosphate binder may be discontinued for subsequent treatment cycles if serum phosphorus levels are <3 after the first treatment with alvocidib and there is no evidence of TLS

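### For AZA + alvocidib patients in Cycles 2+, Protocol Section 5.2.2.1 makes stopping hydration depend on laboratory values while three other places make it optional without condition, and the phosphate binder threshold is inconsistent and lacks a unit

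*Protocol*

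**What the plan says.** Four places in the protocol say when TLS prophylaxis may be relaxed after Cycle 1 for patients receiving azacitidine then alvocidib.

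- **Section 5.2.2.1** treats the three measures together: "pretreatment IV hydration, oral allopurinol, and oral phosphate binder may be discontinued", "if serum uric acid and phosphorus levels are within normal limits and there is no evidence of TLS". Its title and its Day 10 instructions show that the hydration meant is the hydration before alvocidib.
- **Synopsis, Section 4.5.1.1.2 and Appendix A-3 (note j)**, on hydration: "Hydration is optional for subsequent cycles". No laboratory or TLS condition is attached.
- **The same three places**, on the binder. Section 4.5.1.1.2 says "If serum phosphorus levels are <3 after the first treatment with alvocidib and there is no evidence of TLS, phosphate binders may be discontinued"; the Synopsis has the same rule. Appendix A-3 note p says "Oral phosphate binder may be discontinued for subsequent treatment cycles if serum phosphorus levels are <3". None gives a unit.
- **The same three places**, on allopurinol. Section 4.5.1.1.2 says "This may be discontinued for subsequent treatment cycles if uric acid levels are within normal limits and there is no evidence of TLS". The Synopsis and Appendix A-3 note o use the same criterion, and phosphorus is not mentioned.

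SAP Section 20 reproduces Appendix A-3 and so repeats its hydration and binder notes.

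**The concern.** Section 4.5.1.1 names adequate hydration before alvocidib as a preventive measure and lists high uric acid and high phosphorus among the features of TLS. Yet under three of the four texts a patient with either value raised may go without hydration before a Cycle 2+ infusion. Section 5.2.2.1 does call for hydration again, but only once TLS is suspected. A patient with a raised value and no suspicion of TLS falls between the texts.

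Protocol Table 4 shows why the risk is taken seriously: TLS was recorded in 9 of 34, 15 of 47 and 5 of 55 patients in three earlier leukemia studies. Disease, dose and regimen differed, so these figures do not estimate the risk in this trial.

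For the binder, a site cannot tell whether to apply its own normal range or a fixed cut-off whose unit it must guess.

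**Working it through.** The plan gives no figure to reproduce, so the check sets the texts side by side. All cases assume Cycles 2+ and no evidence of TLS.

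| Measure | Section 5.2.2.1 permits stopping if | Synopsis, Section 4.5.1.1.2 and Appendix A-3 permit stopping if |
|---|---|---|
| Hydration before alvocidib | uric acid and phosphorus normal, no TLS | always |
| Phosphate binder | phosphorus normal, no TLS (also uric acid, if read jointly) | phosphorus below 3 (no unit), no TLS |
| Allopurinol | uric acid normal, no TLS (also phosphorus, if read jointly) | uric acid normal, no TLS |

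**Two readings of Section 5.2.2.1.** Its sentence can be read jointly (both values must be normal before any measure stops) or distributively (uric acid governs allopurinol, phosphorus governs the binder).

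**Hydration.** Take uric acid or phosphorus above normal. Three texts let hydration be omitted; Section 5.2.2.1 does not extend its permission to this patient. Hydration is not paired with one analyte, so it stays conditional in one place and unconditional in three under either reading. No assumption about units or ranges is needed.

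**Binder.** Take normal uric acid and phosphorus between 3 and the laboratory's upper limit. Section 5.2.2.1 lets the binder stop; the other three do not. This needs an upper limit above 3 in the unit meant, and the documents give neither unit nor range. If the limit were below 3, the mismatch would run the other way, because the fixed cut-off would admit values above normal. A second case, phosphorus below 3 with raised uric acid, differs only under the joint reading.

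**Allopurinol.** Take normal uric acid and raised phosphorus. The texts differ under the joint reading and agree under the distributive one.

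**Does another clause settle it?** Section 4.5 allows supportive-care dosages to be adjusted; it does not choose a stopping criterion. The institutional discretion in Section 4.5.1.1.3 concerns treatment. Section 5.2.2.1 points to Section 4.5.1.1.2 and Appendix A-3, but only where TLS is suspected, and those are the places with the differing rules.

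**Scope.** SAP Section 8.1 lists two azacitidine cohorts: 3 + 4 = 7 patients. Expansion and Phase 2 would have added up to 25 + 25 = 50; SAP Section 2 records that none enrolled.

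**The case against.** The strongest reply is that no instructions collide. Every text grants a permission, and a site that follows the strictest one complies with all. That stands, and it limits the weight of the point.

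Second, Section 4.5.1.1 links tumor lysis to initial cytoreductive therapy, which fits mandatory hydration in Cycle 1 and optional hydration later. Safeguards also remain: tumor lysis labs are taken around the Day 1 azacitidine and Day 10 alvocidib doses of Cycle 2, Appendix A-3 continues potassium and fluid-loss monitoring, Section 4.5.1.1.2 urges caution with high blast counts, and hydration returns if TLS is suspected. This too stands, and it makes any harm limited.

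Third, Section 5.2.2.1 is one text against three, so the smallest edit would be to make hydration optional there as well. That would restore consistency. It would also remove the only laboratory condition the protocol attaches to stopping a named preventive measure, although the chemistry that the condition needs is already drawn.

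A reader might also infer two stronger points that the documents do not support:

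- That the allopurinol rules conflict outright. They do so only if Section 5.2.2.1 is read jointly, and the distributive reading is a natural one.
- That the binder may be stopped on Days 11-14 of Cycle 1, because the Synopsis and Section 4.5.1.1.2 do not confine their rule to later cycles. Sections 5.2.1.3 and 5.2.1.4 and Appendix A-3 notes e and k fix the binder as daily through Day 14 of Cycle 1.

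**Conclusion.** The inconsistency is real for hydration under either reading of Section 5.2.2.1. For the binder it depends on where the laboratory's upper limit lies relative to 3 in an unstated unit; the missing unit is a defect in itself. For allopurinol the difference depends on the joint reading and should not be counted as established.

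The size is small. The documents give no distribution of uric acid or phosphorus, so the number of patients affected cannot be estimated. A reader might infer that patients were put at risk or that sites received contradictory orders; the permissive wording and the remaining monitoring do not support either inference. Sample size, power, and the DLT and MTD assessment are untouched. This is a minor safety consistency correction, relevant to any continued treatment of the 7 azacitidine patients or reuse of the text.

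**What to change.** 1. In the Synopsis, Section 4.5.1.1.2 and Appendix A-3 note j (and the SAP Section 20 copy), replace the unconditional hydration sentence with the Section 5.2.2.1 condition: hydration before alvocidib may be omitted in Cycles 2+ only if uric acid and phosphorus are not above the upper limit of normal and there is no evidence of TLS. Wording it by the upper limit keeps a low value from blocking the omission. Use the same wording in Section 5.2.2.1.
2. Judge this on the most recent chemistry available before hydration would start, no older than that cycle's Day 1 panel. Section 5.2.2.2 already requires that panel, and it includes both analytes. The Day 10 sample in Section 5.2.2.3 is drawn just before the infusion, so it helps only if taken early enough.
3. In Section 5.2.2.1, tie allopurinol to uric acid and the binder to phosphorus. Use one phosphorus threshold, with its unit, in every place; the sponsor should choose it.

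No new blood test is needed. The first change is more than editorial, because hydration would no longer be optional for patients with raised values. At the Cycle 1 volumes in Section 4.5.1.1.2, they would receive about 250-500 cc of extra fluid before alvocidib, over 1-2 hours at the 500 cc volume.
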